Title: Kovanaze Vs. Articaine in Achieving Pulpal Anesthesia of Maxillary Teeth

NCT #: NCT03962634

Document date: 08/28/2019

Document Type: Protocol and Statistical Analysis Plan

Kovanaze vs. Articaine in Achieving Pulpal Anesthesia of Maxillary Teeth: A Randomized, Open-label, Non-Inferiority Trial

Background:

The words a common man would associate with a dentist are 'pain', 'drill' and 'needle'. This association is unfortunate for dentists because a majority of dental procedures require local anesthesia to ensure patient safety and comfort. In clinical dentistry, local anesthetics are directly injected in various sites of the mouth.

Studies have shown that it is the psychological aspect of seeing the needle or expecting a needle to enter the mouth that scares most patients. From a patient's perspective, the needle has been identified as the most fear provoking part of the dentists' armamentarium. The sight of a sharp, metallic needle entering a protected part of the body greatly increases the anxiety and triggers the 'fight or flight' response. The resulting release of adrenaline might be as much as 40 times the normal levels. This adrenaline burst can result in syncopal episodes that accounts for more than half of medical emergencies in dental practice. Heart attacks and strokes can occur in patients suffering from cardiovascular diseases (hypertension, myocardial infarction, angina, arrhythmia). [1] It is recommended that more medically compromised the patient is, more efforts should be made to reduce anxiety. [2]

The aspirating syringe and needle used today was introduced around 150 years ago. [3] It is estimated that up to 40 million Americans avoid visiting the dentist because of fear of pain and anesthetic injections. [4-6] One study found most patients view the injection as the only painful part of the dental procedure. [7]

In June 2016, an intranasal delivery system of local anesthesia called Kovanaze, gained FDA approval. [8] Kovanaze is available as a 0.2 ml metered spray and is intended to achieve pulpal anesthesia of 5 maxillary teeth on either side of the face. Even though success rates between 83 and 90 % have been reported for adults and children >40kg, FDA label (Section 14.2) provides data for children (>10 kg) indicating that the drug is safe for use in children as long as the dose is adjusted to bodyweight of the child. [9]

- One 0.1 mL spray for patients weighing 10 kg to less than 20 kg;

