- Maximum blood pressure reading of 166/100 mmHg
- Vital pulp (Cold and EPT positive)

Exclusion Criteria:

- History of inadequately controlled hypertension or active thyroid disease
- Five or more nosebleeds in the past month
- Known allergy to oxymetazoline, tetracaine, benzylalcohol or para-aminobenzoic acid
- History of congenital or idiopathic methemoglobinemia
- Taking monoamine oxidase inhibitors, tricyclic antidepressants (e.g. amitriptyline), or non-selective beta adrenergic antagonists (e.g. propranolol)
- Taking oxymetazoline-containing products (i.e., Afrin) in the last 24 hours

- Pregnant and lactating women
- Non vital pulp (Cold and EPT negative)

Study Characteristics:

Design:

Randomized, open label clinical trial

Non-inferiority threshold and Sample size calculation:

The anesthetic efficiency of articaine has been reported in the literature to be around 78 – 88% (Evans et al.). The non-inferiority threshold is the maximum allowable excess of outcome events arising from the novel treatment compared with the standard treatment. The threshold for this study has been selected based on draft guidance set by the FDA (Temple et al.) and was set at 25%. Using nQuery Advisor v7.0, we verified that a sample size of 38 subjects per group would be needed to show a non-inferiority of <25% (one sided alpha of 0.05 and a power of 83%).

Accordingly, each of our study arms will have 90 subjects: 45 in Kovanaze and 45 in Articaine groups.

Accounting for screen failures and dropouts, we will recruit 100 participants in each population totaling 300 for the entire study.

Intervention:

Metered Kovanaze sprays (0.2 ml each spray, St. Renatus) in the nostril on the same side as the tooth of interest. The dose involves:

2 sprays in adult and kids weighing 40 kg or more

1 spray in kids > 6 years but weighing between > 20 kg and < 40 kg

Control:

- Children: 1.0 ml of 4% articaine (containing 1:100000 epinephrine) delivered in the periapex of the tooth of interest by labial/buccal infiltration
- Adults: 1.8ml of 4% articaine (containing 1:100000 epinephrine) delivered in the periapex of the tooth of interest by labial/buccal infiltration

Population:

Our study will evaluate the effectiveness of Kovanaze in three different populations.

Population 1: *Children (aged 6-17 years and weighing >20 kg) requiring specific procedures for treatment of oral disease*

Location: Department of Pediatric Dentistry, 3rd floor, Wood Building

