The biostatistician on the study team ([name]) will generate random sequence using a computer. The randomization will be in block of varying size (4 or 6) and the list will be provided to the following lead faculty who will serve as co-investigators as listed below:

Population 1: Pediatric Dentistry, [name]

Population 2: Endodontics, [name]

Population 3: General Practice, [name]

b. Allocation Concealment:

All random assignments will be placed in sequentially numbered opaque envelopes and will be handled by a staff in the respective department (not a part of the study team). If the participant is found to be eligible for the study, the resident/ student will inform the patient about the study. The team will answer all questions regarding the study and will request consent to participate in the study. After obtaining written patient consent, the department staff (not a member of the study team) will reveal the allocation.

Outcomes:

Patient important outcomes are considered including the primary outcome of completion of intended procedure without rescue anesthetic. This dichotomous outcome (success or failure of anesthesia) is linked to patients' rating of pain on a validated Heft-Parker visual analog scale. The emoji scale will be used for children. Group comparison between the articaine and Kovanaze formulations for anesthetic success will be analyzed by using Fisher's exact test.

Secondary outcomes include objective assessment of hard tissue and soft tissue anesthesia, anxiety scale (STAI-Y6 short form for children and MDAS scale for adults).

[figure not shown]
Adult participants who receive Kovanaze will also be asked to complete a survey to assess the impact of Kovanaze on patient confidence in seeking dental care.

Primary Outcome Measure in Adults:

Proportion of study participants in whom intended dental procedure could be successfully completed without the need for rescue anesthetic.

Heft Parker Scale: Each patient will rate his or her initial pain on a Heft Parker visual analogue scale, a 170-mm line with various descriptive terms. The subjects will be asked to place a mark on the scale where it best described their pain level both at the start and any time during the procedure. To interpret the data, the VAS is divided into the following four categories:

- a. No pain corresponded to 0 mm on the scale.

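### The stated 83% power belongs to 38 per group, but the trial plans 45; at that size power is about 88 to 89% at one-sided 0.05 and about 79 to 82% at one-sided 0.025

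*Combined protocol and SAP*

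**What the plan says.** All the figures stand under 'Non-inferiority threshold and Sample size calculation' in the combined protocol and SAP.

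- The calculation: "we verified that a sample size of 38 subjects per group would be needed to show a non-inferiority of <25" per cent, with "one sided alpha of 0.05 and a power of 83" per cent.
- The planned size: "Accordingly, each of our study arms will have 90 subjects: 45 in Kovanaze and 45 in Articaine groups". Here 'arms' means the three populations.
- The allowance for losses: "Accounting for screen failures and dropouts, we will recruit 100 participants in each population totaling 300 for the entire study".

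The section cites an articaine success range of 78 to 88%. It does not say which value was entered, and it gives no assumed rate for Kovanaze. The Background says of Kovanaze that "success rates between 83 and 90 % have been reported for adults and children >40kg", but the calculation does not refer to this.

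Under 'Outcomes', the analysis is described in one sentence: "Group comparison between the articaine and Kovanaze formulations for anesthetic success will be analyzed by using" Fisher's exact test. No significance level, confidence interval or margin is attached to it.

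**The concern.** The text moves from 38 to 45 per group as if the second number followed from the first, and reports no power for 45. The extra 7 per group do not read as a reserve for losses, because that reserve is made afterwards, from 90 to 100. A reader who takes 83% as the power of this trial has the wrong figure.

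The gap matters because of what the extra patients could buy. The plan sizes the trial at one-sided 0.05 without giving a reason. At that level, a spray that truly succeeds 25 points less often than articaine would be called non-inferior about once in 20 times, in each of three separately randomized populations. If 45 per group can carry one-sided 0.025 at close to the intended power, that risk can be halved without recruiting anyone else.

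The plan also has no stated rule for declaring non-inferiority. As named, Fisher's exact test compares the two proportions for equality and does not use the 25-point margin.

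**Working it through.** **Inputs.** From the sample size section: margin 0.25 (read as an absolute difference), one-sided alpha 0.05, power 83%, 38 per group calculated, 45 per group planned. The success rates are assumptions, because the plan does not state them. One-sided 0.025 is this review's comparator and does not appear in the documents.

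**Formula** (normal approximation, unpooled variance, pc = articaine, pt = Kovanaze):

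SE = sqrt{[pc(1-pc) + pt(1-pt)] / n}

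power = Phi{[0.25 - (pc - pt)] / SE - z}, with z = 1.645 at 0.05 and 1.960 at 0.025.

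**Step 1: reproduce 38.**

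- 78%/78%: SE = sqrt(0.3432/38) = 0.0950; 0.25/0.0950 = 2.631; less 1.645 = 0.986; power 83.8%. With 37 per group it is 82.9%, so 38 is the smallest size reaching 83%.
- Articaine 83%, Kovanaze 81%: SE = sqrt(0.2950/38) = 0.0881; 0.23/0.0881 = 2.610; less 1.645 = 0.965; power 83.3%. With 37 it is 82.4%, so this pair also returns 38.

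The plan's figure is reproducible, but more than one set of inputs gives it.

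**Step 2: power at 45 per group.** The enumerated column sums exact binomial probabilities over all outcomes for the score (Farrington-Manning) test.

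| Articaine / Kovanaze | Level | Formula | Enumerated |
|---|---|---|---|
| 78% / 78% | 0.05 | 88.8% | 88.8% |
| 78% / 78% | 0.025 | 81.7% | 81.6% |
| 83% / 81% | 0.05 | 88.4% | 87.9% |
| 83% / 81% | 0.025 | 81.1% | 79.2% |

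Scaling from exactly 83% at 38, without assuming rates: (1.645 + 0.954) x sqrt(45/38) = 2.828, which gives 88.2% at 0.05 and 80.7% at 0.025.

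So power at 0.025 is about 1 to 4 points below the stated 83%. Reaching 83% at 0.025 needs (1.960 + 0.954)^2 x 0.3432/0.0625 = 46.6, so 47 per group, at 78%/78%. At 83%/81% it needs (1.960 + 0.954)^2 x 0.2950/0.0529 = 47.4, so 48.

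**Step 3: false non-inferiority risk.** With 45 per group and Kovanaze truly 25 points worse (articaine 78, 83 or 88%), the enumerated risk of the score test is 5.1 to 5.3% at 0.05 and 2.5 to 2.7% at 0.025. For three independent populations all exactly at the margin, the risk of at least one false finding is 1 - 0.95^3 = 14.3% against 1 - 0.975^3 = 7.3%.

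**Step 4: less favourable truths** (45 per group, enumerated; the rates are assumptions).

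| Articaine / Kovanaze | Power at 0.05 | Power at 0.025 |
|---|---|---|
| 83% / 78% | 77% | 65% |
| 78% / 73% | 72% | 61% |
| 50% to 60% in both | 77 to 78% | 70 to 71% |

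**The case against.** **No arithmetic error.** The plan ties 83% to 38 per group and never claims it for 45. Enrolling more than the minimum is conservative. This stands: the defect is an unreported power figure and an unexplained step.

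**The stricter level is a preference.** The plan openly sets one-sided 0.05 for its calculation, and nothing in the documents requires 0.025. This also stands. The case for 0.025 rests on how little power it costs at this size, not on a rule the plan has broken.

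**The extra patients may be needed.** A reader might infer that one-sided 0.05 serves no purpose once 45 per group are enrolled. The documents do not support that. If Kovanaze is truly 5 points worse (78% against 83%), the stricter level takes power from 77% to 65%. The section on Population 1 expects the depth of anesthesia to vary with disease state and procedure, and Population 2 enters with symptomatic irreversible pulpitis and moderate to severe pain, so the planning rates may not hold everywhere.

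**45 may not be the number analyzed.** The step from 90 to 100 must cover both screen failures and dropouts. Population 2 also excludes teeth without vital coronal pulp on access, which can be seen only after allocation. If the analyzed number fell to 38 per group, power at 0.025 would be about 73 to 75%. The risk is fair, but the text places the allowance after 45, so 38 is not the planned size.

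**The three-population risk.** A reader might infer that the trial carries a 14% chance of a false claim. That needs all three populations to lie exactly at the margin. The plan treats them as separate settings and describes no claim that rests on any one of them succeeding. The figure is a worst case only.

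**Conclusion.** The point holds as a reporting gap with a cheap improvement attached. The 83% describes 38 per group. For the 45 planned, power under inputs that return 38 is about 88 to 89% at one-sided 0.05 and about 79 to 82% at one-sided 0.025. The planned size nearly, but not fully, supports the stricter level, at which the false non-inferiority risk per population is about 2.5% instead of about 5%.

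This rests on reading 45 as the size before losses, on a 25-point absolute margin, and on true rates that are equal or within about 2 points. It does not rest on 78% in both groups. That pair is tempting to read as the sponsor's input because it returns 38, but 83%/81% returns 38 as well and comes closer to the stated 83%. The error risks in the working are those of a score test, because the plan gives no level or margin for its own analysis.

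**What to change.** 1. In the sample size section, state the success rates actually entered for articaine and Kovanaze, and give the power for 45 per group beside the calculation for 38. Only the sponsor can supply the rates; they should not be filled in from a back-calculation.
2. Under 'Outcomes', add a decision rule. In each population, non-inferiority is concluded if the lower limit of the two-sided 95% confidence interval for the difference in success (Kovanaze minus articaine) lies above -25 points. Name the interval method; a score interval would match the enumerated figures. Fisher's exact test can remain as a supporting comparison.
3. If one-sided 0.05 is kept, use the two-sided 90% interval in the same rule and restate power as about 88 to 89% for 45 per group.

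The cost is wording, with no added patients. Choosing the 95% interval gives up about 7 to 9 points of power at the planning rates. Power would be about 65% (instead of 77%) if Kovanaze is truly 5 points worse at 78% against 83%, and about 70% if success is near 50 to 60% in both groups. The sponsor should weigh that loss openly when choosing between the two levels.

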Eligible procedures: Procedures that would require local anesthesia include direct restorations (fillings), pulpotomy or pulpectomy (partial or complete removal of pulp) and placement of stainless steel crowns.

The standard of care in Department of Pediatric Dentistry is to administer nitrous before start of the treatment to alleviate patient anxiety. We will follow routine clinical protocol to titer the dose of nitrous oxide to individual patient needs.

Additionally, we hypothesize that the degree and depth of anesthesia would vary based on the initial disease state as well as the intended procedure. Accordingly, impact of the anesthesia will be analyzed at the completion of study using subgroup analysis.

Population 2: Symptomatic adults (>18 years) with symptomatic irreversible pulpitis

Location: Department of Endodontics, 2nd floor, Lyons Building

Eligible procedures:

Root canal treatment in teeth with significant decay but presenting with signs and symptoms of irreversible pulpitis (symptomatic)

Additional Inclusion Criteria:

- Tooth with a diagnosis of symptomatic irreversible pulpitis with or without periapical periodontitis
- Diagnosis is confirmed by history of spontaneous pain or prolonged (lingering) pain on application of cold or electronic pulp testing
- Tooth should have moderate to severe pain at the study onset (>54 on Heft Parker VAS scale)

Additional Exclusion criteria:

- Tooth with no response to cold / electronic pulp testing
- Tooth with periapical pathosis as seen in the radiograph
- Tooth with no vital coronal pulp tissue upon access

Population 3: Asymptomatic adults (>18 years) requiring restorations or crowns

Location: Department of General Practice, 2nd floor, Lyons/ Wood Building

Eligible procedures:

Direct and indirect restorations in teeth with significant decay but presenting with signs and symptoms of healthy pulp or reversible pulpitis

Additional Inclusion Criteria:

- Asymptomatic maxillary tooth with a diagnosis of primary or secondary dental caries extending more than 70% the thickness of dentin as seen in the radiograph

Additional Exclusion criteria:

- Tooth with no response to cold / electronic pulp testing
- Tooth with periapical pathosis as seen in the radiograph
- Endodontically treated tooth

Randomization

a. Sequence Generation:

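### In children, the hypothesis that anesthesia varies by procedure and disease state rests on an unspecified subgroup analysis, and the primary comparison leaves procedure out

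*Combined protocol and SAP*

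**What the plan says.** The Population 1 text on eligible procedures lists fillings, pulpotomy or pulpectomy, and stainless steel crowns. It then states that "we hypothesize that the degree and depth of anesthesia would vary based on the initial disease state as well as the intended procedure" and gives the analysis in one sentence: "Accordingly, impact of the anesthesia will be analyzed at the completion of study using subgroup analysis". It does not define procedure classes or levels of disease state. It does not name the outcome, the model, a test of difference between subgroups, or a multiplicity rule.

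The Outcomes section compares anesthetic success between the two formulations by Fisher's exact test and mentions no adjustment. The Randomization section gives blocks of 4 or 6 and names no stratification factor within a population.

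The size comes from the overall non-inferiority comparison alone: "a sample size of 38 subjects per group would be needed to show a non-inferiority of <25" percent, with "one sided alpha of 0.05 and a power of 83" percent. The plan then states that "each of our study arms will have 90 subjects: 45 in Kovanaze and 45 in Articaine groups", where arms evidently means the three populations. Adults, unlike children, are divided by disease state into Populations 2 and 3.

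**The concern.** The hypothesis is about a difference between procedures and between disease states. If the subgroup analysis is carried out in the usual way, as a Kovanaze-articaine comparison inside each subgroup, it answers another question. A favorable result in one subgroup and an unfavorable one in another is not evidence that the subgroups differ. With small subgroups that pattern is likely by chance, so an apparent failure in, say, pulp therapy could be an artefact of numbers.

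Procedure is also known before treatment and is expected by the plan itself to matter, yet the primary comparison does not use it. Specific Aim 1 singles out procedures other than fillings, so procedure type is close to the study's main question.

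**Working it through.** **Inputs from the documents.** Margin 25 points, one-sided alpha 0.05, and articaine success of 78-88% (section on threshold and sample size); 45 per arm in each population.

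**Assumptions, not in the documents.** Equal true success in both arms unless stated; equal class sizes (unequal sizes lower power further); anesthetic success as the outcome; two-sided 0.05 for the between-procedure and interaction tests; normal approximations throughout.

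**1. The plan's own figure.** Power = Φ(0.25/SE − 1.645), with SE = √(2p(1−p)/n). At p = 0.78 and n = 38, SE = √(0.3432/38) = 0.0950, so power = Φ(2.631 − 1.645) = 83.8%, against the stated 83%. The figure of 38 per group is therefore reproduced at the low end of the quoted range. That rate is inferred, because the plan does not say which was used.

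**2. Non-inferiority inside a subgroup, arms truly equal.** The same formula gives:

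| Equal classes | n per arm per class | p = 0.78 | p = 0.83 | p = 0.88 |
|---|---|---|---|---|
| Three | 15 | 50.3% | 57.1% | 67.8% |
| Two | 22 | 63.9% | 71.3% | 81.8% |

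The chance that at least one of three classes misses is 1 − 0.503³ = 87% at p = 0.78 and 1 − 0.678³ = 69% at p = 0.88. With two classes it is 1 − 0.639² = 59% and 1 − 0.818² = 33%.

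**3. The hypothesis as a main effect, arms pooled, 45 versus 45.** At 80% success, SE = √(2 × 0.16/45) = 0.084. The difference detectable with 80% power is 2.80 × 0.084 = 0.24, or about 24 points. With 78-88% success in the better class, power is 53-63% for a 20-point difference and 85-91% for 30 points.

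**4. Arm-by-procedure interaction, two equal classes (22.5 per arm per class).** SE = √(4p(1−p)/22.5). The 95% half-width is 1.96 × 0.175 = 34 points at p = 0.78 and 1.96 × 0.137 = 27 points at p = 0.88. Power for a 20-point difference in treatment effect is 19-25%, and for 30 points 37-48%. Power of 80% for 20 points would need roughly 420-596 children.

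**5. Gain from stratifying the primary difference.** With two equal classes differing by d around average success p̄, the fractional variance cut is 0.25d²/[p̄(1−p̄)].
- At p̄ = 0.80: 0.25 × 0.04/0.16 = 6% for 20 points, and 0.25 × 0.09/0.16 = 14% for 30 points.
- With the better class at 83-88%, the cuts are about 5-6% for 20 points and 10-11% for 30.
- Effect on power at 45 per arm and p = 0.78: 0.25/√(0.3432/45) = 2.863, so the unadjusted power is Φ(2.863 − 1.645) = 88.8%. A 6% cut gives Φ(2.863/√0.94 − 1.645) = 90.5%. A 14% cut gives Φ(2.863/√0.86 − 1.645) = 92.5%.

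**6. Stratifying the list.** At p = 0.83 the interaction SE is 0.158 with a stratified list and averages 0.159 without. Under simple 45/45 allocation, a gap between arms of 15 points or more in the share of a procedure class has a probability of about 12% if the class is one third of children and 21% if it is half.

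**The case against.** The strongest reply is that the plan has not committed itself to the analysis criticized here. It never says that the arms will be tested within each subgroup or that non-inferiority will be concluded for a subgroup, and the 25-point margin is attached to the overall comparison. That is correct. The figures in step 2 show what would happen under that reading; they are not the power of a claim the plan makes.

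A reader might also infer three stronger points that the documents do not support:

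- *That 90 children cannot test the hypothesis.* Its wording is naturally prognostic: anesthesia varies by procedure or disease state. On that reading a 30-point difference between equal halves is found with 85-91% power. Only moderate differences, and interactions, are out of reach.
- *That the missing stratification is the cause.* Step 6 shows that it barely affects the interaction. The limits are sample size and missing specification.
- *That the unadjusted primary comparison discards a known prognostic factor, or is invalid.* The factor is hypothesized, not shown. An unadjusted comparison is valid under randomization, and the plan already enrolls 45 against a calculated 38. Large precision gains need extreme gaps: 40 points around 80% means 100% versus 60% success.

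What remains is that the method is undefined, that its usual form does not estimate what is hypothesized, and that two inexpensive changes would improve on it.

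**Conclusion.** The concern holds in a limited form. The stated hypothesis has no defined analysis. Reading it from arm comparisons within subgroups would give unreliable results: 50-68% probability of showing non-inferiority per class with three equal classes and 64-82% with two, when the arms do not differ. The same 90 children can support a between-procedure estimate, with 80% power for about 24 points when split 45 versus 45. Leaving procedure out of the primary comparison costs some precision but does not bias it; the loss is about 5-14% of variance if success differs by 20-30 points between equal classes, and close to nothing if procedure does not matter.

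These sizes rest on equal classes, on success rates taken from the quoted 78-88% range, and on success as the outcome. The hypothesis also speaks of depth, but timed depth testing is listed only among the adult secondary outcomes, so the intended outcome in children needs to be named.

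**What to change.** 1. **Primary comparison in Population 1.** Estimate the success difference stratified by planned procedure class (pulpotomy or pulpectomy versus restoration or crown), and set its one-sided 95% confidence bound against the 25-point margin. Record the class before allocation is revealed, with a rule for a child planned for both. Stratifying the randomization list by the same factor is optional and adds balance only.
2. **Hypothesis on procedure.** Replace the subgroup analysis with the between-procedure difference in success, adjusted for arm, with its interval. Report the arm-by-procedure interaction as exploratory, with its interval, and say in advance that this will be roughly ±27 to 34 points. Make no non-inferiority claim from any subgroup.
3. **Disease state.** Define its levels for children and examine it in a separate model.

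The cost is SAP wording and one field recorded before allocation, with no extra participants. The downside is sparse data: at 80% success, 90 × 0.20 = 18 failures are expected, so the models must stay small. This is why only two procedure classes are used and disease state is kept apart.

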5. What is the most important deciding factor for you to choose NASAL SPRAY ANESTHETIC for your dental needs?

Cost Fear and Anxiety

6. How much extra money would you be willing pay for the NASAL SPRAY ANESTHETIC?

\$20 \$50 Up to \$100 It is not worth paying extra

7. Did your experience with the NASAL SPRAY ANESTHETIC change your outlook towards receiving future dental care?

Nothing changed; Still scared of dental visits This appointment was better but am still concerned about my future visits This appointment definitely eased my apprehension of future dental visits

8. If you had known that there was an option of NASAL SPRAY ANESTHETIC, would you have sought dental care early?

Definitely No Maybe Definitely Yes

5. Survey after 24 hours:

A short one question about the side effects of local anesthetic will be asked to the patient in person or over phone at 24 hours.

Did you suffer any of the following side-effects after your dental visit?

- nasal drainage,
- nasal congestion,
- burning,
- pressure,
- sinus congestion,
- pain and soreness at the site of the anesthesia (scored from 1-10)
- Numbing or tingling in throat
- other (Specify)_____

Flow of research study visit in adults (>18 years):

Screening of EHR will be done to identify potential study participants on a routine clinical visit. During the study visit the study related procedures would be preformed in the following order:

1. Go over the study details, answer participant questions and obtain informed consent
2. Administer MDAS anxiety survey
3. Ask patient to rate pain (if present) in the Heft Parker Scale
4. Reveal allocation (Kovanaze or Articaine)
5. Take baseline BP and heart rate
6. Administer local anesthetic
7. Wait for patient to signal achievement of meaningful anesthesia (using stop watch)
8. Map the extent of soft tissue and hard tissue anesthesia in data collection form
9. Proceed with the intended procedure
10. Assign anesthetic **failure** if subject perceives pain after start of procedure. Record the failure in data collection form and proceed with rescue anesthetic to complete the procedure
11. Assign anesthetic **success** if local anesthesia was adequate to complete the intended procedure without need for rescue anesthetic. Record in data collection form
12. Administer MDAS survey for all participants
13. Administer satisfaction questionnaire to subjects in Kovanaze group only
14. Take end of appointment BP and heart rate

Primary Outcome Measure in Children:

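### The randomization list goes to a co-investigator in each recruiting department, and nothing keeps the list-holders out of recruitment

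*Combined protocol and SAP*

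**What the plan says.** The relevant text is in the two parts of the Randomization section of the combined protocol and SAP, read with the visit flows.

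- **Sequence generation.** The study biostatistician produces a computer-generated sequence in blocks of 4 or 6. Then "the list will be provided to the following lead faculty who will serve as co-investigators as listed below", with one person named for each of Pediatric Dentistry, Endodontics and General Practice. The Location section gives these same three departments as the study sites.
- **Concealment.** "All random assignments will be placed in sequentially numbered opaque envelopes and will be handled by a staff in the respective department"; these staff are described as outside the study team.
- **Approach and consent.** Once a patient is judged eligible, "the resident/ student will inform the patient about the study". Then: "The team will answer all questions regarding the study and will request consent to participate in the study".
- **Reveal.** "After obtaining written patient consent, the department staff (not a member of the study team) will reveal the allocation". The adult and child visit flows keep the same order, with consent at step 1 and allocation at step 4.
- **Screening.** Both visit flows say "Screening of EHR will be done to identify potential study participants on a routine clinical visit", without naming who does it. Who judges eligibility is not stated either.
- **Blinding.** The Design line reads "Randomized, open label clinical trial".

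**The concern.** Revealing the allocation only after consent, through staff outside the team, protects a trial on one condition: nobody who influences screening, eligibility or consent knows the next assignment. The plan sets up that safeguard and, one paragraph earlier, gives the full sequence to study-team members in every recruiting department. An opaque envelope conceals nothing from someone who holds the list.

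A person who knows the next assignment can, without intending to, decide whom to approach, how firmly to apply a borderline criterion, or when to book a patient. The arms can then differ in the kind of case they contain. Because the trial is open label, blinding offers no second line of defence. Case mix plausibly matters here: for children (Population 1) the plan itself expects the result of anesthesia to depend on the starting disease and the procedure. It plans a subgroup analysis for this, but does not describe it as an adjustment of the primary Fisher's exact comparison. Populations 2 and 3 have tighter entry criteria and no such statement.

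**Working it through.** **Reading the text.** The plan states no figure on this point, so the first check is whether the two subsections fit together.

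1. The list goes to co-investigators, who are by definition members of the study team.
2. The envelopes go to people who are not. The evident purpose is to keep the team from knowing the next assignment.
3. The two steps can be consecutive if the faculty receive the list only so that envelopes can be filled. The plan does not say this. It gives no reason for the faculty to have the list and does not say who fills the envelopes or what happens to the list afterwards.
4. Consent is requested by the team, and screening and eligibility have no named actor. No sentence excludes the list-holders from any of these steps.

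**How much foreknowledge the list adds.** Inputs: 90 patients per population, 45 per group (Non-inferiority threshold and Sample size calculation); blocks of 4 or 6 (Sequence Generation). Assumption: equal numbers of the two block sizes, as the plan gives no ratio. The comparison is with an observer who has no list but sees all past assignments.

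*Correct guesses.* The observer guesses the arm that is behind and is right half the time at ties. All sequences in a block are enumerated:

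- Block of 4: 17/6 = 2.833 of 4, or 70.8%.
- Block of 6: 41/10 = 4.1 of 6, or 68.3%.
- One of each: (17/6 + 41/10)/10 = 52/75 = 69.3%.
- For 90 patients: 90 × 52/75 = 62.4.
- Outer bounds: all blocks of 6, 90 × 4.1/6 = 61.5; all blocks of 4, 90 × 2.833/4 = 63.75.

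A list-holder knows 90, so the list adds 90 − 62.4 = 27.6 (bounds 26.25 to 28.5). The rule uses only the running imbalance, so the observer need not know where blocks begin.

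*Assignments known with certainty.* If each block's size is known, an assignment is certain once one arm is used up:

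- Block of 4: 4/3 of 4 = 33.3%.
- Block of 6: 3/2 of 6 = 25.0%.
- One of each: (4/3 + 3/2)/10 = 17/60 = 28.3%, or 25.5 of 90.

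If the observer knows only that sizes are 4 or 6, and not their order, 20,000 simulated lists of nine blocks of each size (9 × 4 + 9 × 6 = 90) in random order give a mean of 5.06 of 90, or 5.6% (standard error 0.02).

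| Per population of 90 | No list, block order unknown | No list, each block's size known | With the list |
|---|---|---|---|
| Expected correct guesses (arm-behind rule) | 62.4 | 62.4 (rule ignores block size) | 90 |
| Known with certainty | about 5 | 25.5 | 90 |

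**The case against.** The strongest reply is that the adjacent text largely deals with the problem. A list followed by envelopes is a natural order of work, the envelope-holders are outside the team, the reveal comes after written consent, and the only people named as approaching patients are residents and students. On this reading what is missing is a detail of who fills the envelopes, not a faulty design. Nothing shows that the lead faculty will recruit, and screening written in the passive is ordinary protocol language. In Populations 2 and 3 the pain, radiographic and pulp-test criteria leave less room for discretion.

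Much of this is fair, and it sets the limits of the point: the risk is potential, not demonstrated. But sending the list to co-investigators is a stated rule and not merely a silence, and the envelope procedure does not reach people who hold the list. Tight criteria limit who qualifies; they do not limit who is approached or when.

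The figures also deserve caution. That a list-holder knows all 90 is simply what having a list means. The comparison assumes an observer who sees every past assignment, which the plan does not say. The all-4 and all-6 cases are only outer bounds, since the plan mixes sizes and 90 is not divisible by 4. An observer who also knew there were nine blocks of each size would be certain of about 6.7 assignments rather than 5. None of this changes the conclusion. Finally, an unadjusted Fisher's exact test is valid when concealment is sound; its use is not evidence of a flaw.

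**Conclusion.** The concern holds. The plan directs the full sequence to a co-investigator in each recruiting department and places no limit on that person's part in screening, eligibility or consent, so its own concealment procedure does not keep upcoming assignments from the study team. The gain in correct foreknowledge is about 28 of 90 assignments per population, and certain knowledge rises from about 5 (or 25.5) to 90, given equal numbers of the two block sizes and an observer who sees all past assignments. These numbers measure foreknowledge, not bias. No breach is shown, and neither the direction nor the size of any bias can be derived from the documents. Confidence is high about what the text says and leaves open. The change should be made because the exposure is avoidable and cheap to remove.

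**What to change.** Replace only the clause that sends the list to the lead faculty, and reword the sentence so that they remain named as departmental leads. The new text should say that:

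1. the biostatistician, or another person with no role in recruitment, prepares the sealed, numbered opaque envelopes and sends only these to the non-study department staff already described;
2. no one who screens, judges eligibility, approaches patients or obtains consent has access to the list;
3. if the faculty must hold the list, the reason is given and they take no part in those steps.

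If they were meant to receive it only for envelope filling, items 2 and 3 say so explicitly.

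The cost is two or three sentences and a little envelope preparation. Block sizes, sample size, analysis and clinical procedures are unchanged. The predictability that comes from blocking itself, about 69% correct guesses for someone who sees all past assignments, remains.
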